Central monitoring: Study-specific monitoring plans are specified per site, with the only difference between sites whether the site submits source data on paper or provides the coordinating center multi-site team remote access to that site's local electronic medical record. Centralized monitoring will occur minimally quarterly, no more frequently than monthly. Monitoring will be centralized, including data reporting and research sample acquisition. The coordinating center multi-site coordinator will perform on-site and/or remote monitoring visit within the first three months of enrollment of the first subject. Quarterly monitoring visits will occur (on site up to once per year and at least three times remotely) until subject follow-up is terminated. Monthly reviews of data will be conducted to ensure compliance or identify discrepancies; specifically, to assess compliance with the protocol, verify informed consent forms, verify compliance with SAE reporting procedures, monitor the tracking of study drug (pharmacy visit, storage and accounting of study drug), retrieve regulatory documentation, and perform quality control by comparing data from the CRF to the source documents of the center.

Auditing

For sites with an auditing mechanism in place that are able to share documentation of their auditing standards and processes followed, an agreement may be requested for the site to perform local auditing and provide formal audit reports to the coordinating center.

23. References

1. X. Li, S. Xu, M. Yu, K. Wang, Y. Tao, Y. Zhou, J. Shi, M. Zhou, B. Wu, Z. Yang, C. Zhang, J. Yue, Z. Zhang, H. Renz, X. Liu, J. Xie, M. Xie, J. Zhao, Risk factors for severity and mortality in adult COVID-19 inpatients in Wuhan., *J. Allergy Clin. Immunol.* (2020), doi:10.1016/j.jaci.2020.04.006.
2. D. Wang, B. Hu, C. Hu, F. Zhu, X. Liu, J. Zhang, B. Wang, H. Xiang, Z. Cheng, Y. Xiong, Y. Zhao, Y. Li, X. Wang, Z. Peng, Clinical Characteristics of 138 Hospitalized Patients with 2019 Novel Coronavirus-Infected Pneumonia in Wuhan, China, *JAMA - J. Am. Med. Assoc.* **323**, 1061–1069 (2020).
3. H. Shi, X. Han, N. Jiang, Y. Cao, O. Alwalid, J. Gu, Y. Fan, C. Zheng, Radiological findings from 81 patients with COVID-19 pneumonia in Wuhan, China: a descriptive study, *Lancet Infect. Dis.* **20**, 425–434 (2020).

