To compare the incidence of mechanical ventilation or death in subjects with severe COVID-19 given placebo or oral duvelisib.	The primary end-point is a composite endpoint of mechanical ventilation or death within 4 weeks of randomization.
Secondary	
Secondary Objectives are to compare the duvelisib cohort to the placebo cohort with respect to:
 
1) Days to recovery as assessed by ACTT endpoints as the time to recovery (Day 1 through Day 29) to satisfy a score of ≥ 5 from the following eight categories from the NIAID ordinal scale. The scale is as follows: 1. Death; 2. Hospitalized, on invasive mechanical ventilation or extracorporeal membrane oxygenation (ECMO); 3. Hospitalized, on non-invasive ventilation or high flow oxygen devices; 4. Hospitalized, requiring supplemental oxygen; 5. Hospitalized, not requiring supplemental oxygen - requiring ongoing medical care (COVID-19 related or otherwise); 6. Hospitalized, not requiring supplemental oxygen - no longer requires ongoing medical care; 7. Not hospitalized, limitation on activities and/or requiring home oxygen; 8. Not hospitalized, no limitations on activities.2) Duration of hospitalization3) Death within 29 days of randomization4) ICU transfer within 29 days of randomization5) ECOG performance status at day 15 and 29 of randomization6) Incidence of grade III-V adverse events or SAEs (as defined by CTCAE version 5)7) Documented secondary bacterial or viral infection within 29 days of randomization.8) Mean frequencies of Th1 and Th17 T cells in blood mononuclear cells at 1, 2 and 4 weeks9) Mean levels of inflammatory serum biomarkers at 1, 2 and 4 weeks10) Gene expression profiles of T cells at 1, 2 and 4 weeks

OBJECTIVES	ENDPOINTS
11) Median titers of IgG antibodies to SARS-CoV-2 at 4 weeks 12) Survival at day 50-60 after randomization	

3. Background

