16.1 Safety Analyses

Adverse event data will be described and graded per the NCI CTCAE v5.0 guidelines. For AE that are not listed in the NCI CTCAE v5.0 guidelines, grade 3 AEs are defined as events that interrupt usual activities of daily living, or significantly affects clinical status, or may require intensive therapeutic intervention. Severe events are usually incapacitating. For each adverse event, information to be collected includes event description, time of onset, clinician assessment of severity, relationship to study product (assessed only by those with the training and authority to make a diagnosis), and time of resolution/stabilization of the event. Regardless of relationship, all AEs will be recorded with start dates occurring any time after patient receives any duvelisib/placebo. At each study visit, the investigator will inquire about the occurrence of AE/SAEs since the last visit. Events will be followed for outcome information until resolution or stabilization.

Any medical condition that is present at the time that the participant is screened will be considered as baseline and not reported as an AE. However, if the study participant's condition deteriorates at any time during the study, it will be recorded as an AE. Changes in the severity of an AE will be documented to allow an assessment of the duration of the event at each level of severity to be performed. AEs characterized as intermittent require documentation of onset and duration of each episode.

The maximum grade for each type of toxicity will be recorded for each patient, and frequency tables will be reviewed to determine toxicity patterns. Adverse events will be summarized and described within each cohort. They will initially be reviewed regardless of attribution, but also whether they are possibly, probably, or definitely related to treatment. In addition, we will review all adverse event data that are graded as 3, 4, or 5 and classified as either "unrelated" or "unlikely to be related" to study treatment in the event of an actual relationship developing. The incidence of severe adverse events or toxicities will be described. We will assess the proportion of patients who experience grade 3 or higher non-hematologic toxicity. To assess tolerability, we will also capture the proportion of patients who go off treatment due to adverse events.

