16.2 Adverse Event and Serious Adverse Event Reporting

Definition of Adverse Events (AE)

The ICH defines an adverse event as any unfavorable and unintended sign, including laboratory findings, symptoms or diseases temporally associated with the use of an investigational product. Adverse event severity will be graded per the using the CTCAE version 5 for toxicity and adverse event reporting.

Protocol Title: Duvelisib Ameliorates Manifestations of Pneumonia in Established Novel Coronavirus Infection (DAMPEN-CI)

Any adverse events, either observed by the investigator or reported by the patient, should be documented, including the intensity and duration of the AE, what steps were taken in regard to duvelisib and the outcome.

The principal investigator must review any laboratory abnormality for clinical significance. If the abnormality is deemed to be clinically significant, then the adverse event will be reported along with the actions taken in regard to duvelisib and the outcome of the event. All AE's will begin recording at the beginning of enrollment until withdrawal and/or completion of the clinical trial.

Definition of Serious Adverse Events (SAE)

An adverse event (AE) or suspected adverse reaction is considered "serious" if, in the view of either the investigator or sponsor, it results in any of the following outcomes:

- Death
- Life-threatening adverse event
- Inpatient hospitalization or prolongation of existing hospitalization
- A persistent or significant incapacity or substantial disruption of the ability to conduct normal life functions, or a congenital anomaly/birth defect.
- Important medical events that may not result in death, be life-threatening, or require hospitalization may be considered serious when, based upon appropriate medical judgment, they may jeopardize the participant and may require medical or surgical intervention to prevent one of the outcomes listed in this definition. (Examples of such medical events include allergic bronchospasm requiring intensive treatment in an emergency room or at home, blood dyscrasias or convulsions that do not result in inpatient hospitalization, or the development of drug dependency or drug abuse).

Study-Specific AE/SAE Reporting

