- Due to the wide array of symptoms experienced by patients hospitalized with COVID-19, it is not feasible or informative to record and assess all possible symptoms and lab test results for AE/SAE grading in this study. Hence AE/SAE grading and reporting will be limited to lab tests that might reflect effects of study drug exposure including bilirubin, ALT, ALK PHOS, AST, leukopenia, lymphopenia, anemia, and thrombocytopenia. Symptomatic AE/SAE grading and reporting will focus on the following: diarrhea, bradycardia, symptoms requiring ICU admission and mechanical ventilation, symptoms requiring repeat hospitalization, or death. Non-clinically relevant AEs (Grade 1) will not be included on AE logs or AE reporting documents.

Classification of an Adverse Event

Severity of Event

For both AE's and SAE's the investigator must assess the severity of the event. The severity of the event will be graded based off the patient's symptoms using the Common Terminology Criteria for Adverse Events (CTCAE Version 5.0):

https://ctep.cancer.gov/protocoldevelopment/electronic_applications/docs/CTCAE_v5_Quick_Reference_5x7.pdf.

The terms "severe" and "serious" are not synonymous. Severity refers to the intensity of an AE (as in mild, moderate, or severe pain); the event itself may be of relatively minor medical significance (such as severe headache). "Serious" is a regulatory definition and is based on patient or event outcome or action criteria usually associated with events that pose a threat to a patient's life or vital functions. Seriousness (not severity) serves as the guide for defining regulatory reporting obligations

Relationship to Study Intervention

All adverse events (AEs) must have their relationship to study intervention assessed by the clinician who examines and evaluates the participant based on temporal relationship and his/her clinical judgment. The degree of certainty about causality will be graded using the categories below. In a clinical trial, the study product must always be suspect.

Expectedness

Principal Investigator will be responsible for determining whether an adverse event (AE) is expected or unexpected.

An **expected** adverse event is those that have previously identified resulting from administration of the study drug. These include, but not limited to, AE's that are listed in the AE list, stated on the informed consent document or listed on the investigator's brochure.

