7. Outcome (not recovered/not resolved, recovered/resolved, recovering/resolving, recovered/resolved with sequelae, fatal, unknown)

Protocol Title: Duvelisib Ameliorates Manifestations of Pneumonia in Established Novel Coronavirus Infection (DAMPEN-CI)

If the event worsens the event should be reported a second time in the CRF noting the start date when the event worsens in toxicity. For grade 3 and 4 adverse events only, if improvement to a lower grade is determined a new entry for this event should be reported in the CRF noting the start date when the event improved from having been Grade 3 or Grade 4. For phase I studies any AE that constitutes a DLT should be reported like a grade 3 and 4 adverse event. All adverse events should be treated appropriately. If a concomitant medication or non-drug therapy is given, this action should be recorded on the Adverse Event CRF.

Once an adverse event is detected, it should be followed until its resolution or until it is judged to be permanent, and assessment should be made at each visit (or more frequently, if necessary) of any changes in severity, the suspected relationship to the study treatment, the interventions required to treat it, and the outcome. Laboratory abnormalities that constitute an Adverse event in their own right (are considered clinically significant, induce clinical signs or symptoms, require concomitant therapy or require changes in study treatment), should be recorded on the Adverse Events CRF.

Laboratory abnormalities, that do not meet the definition of an adverse event, should not be reported as adverse events.

A Grade 3 or 4 event (severe) as per CTCAE does not automatically indicate a SAE unless it meets the definition of serious as defined below and/or as per investigator's discretion. A dose-hold or medication for the lab abnormality may be required by the protocol in which case the lab abnormality would still, by definition, be an adverse event and must be reported as such. Any serious adverse event, or follow up to a serious adverse event, including death due to any cause whether or not related to the study drug, must be **submitted on an SAE form** and assessed by PI in order to determine reporting criteria to regulatory authorities, IRB, DSMC, FDA.

All serious adverse events collected during this time frame will also be reported to Verastem.

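### On the secondary endpoint of grade III-V AEs or SAEs, benefit on COVID-19 can cancel drug toxicity, because ventilation, ICU admission and death count towards it

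*Combined protocol and SAP*

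**What the plan says.** Section 2 lists among the secondary endpoints "Incidence of grade III-V adverse events or SAEs (as defined by CTCAE version 5"). Section 15.1 says categorical secondary endpoints will be compared between arms by Fisher's exact test, and names no significance level for them.

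Four provisions in Section 16 bring disease progression into that count:

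- Section 16.2 (study-specific reporting) limits symptomatic AE/SAE reporting to "diarrhea, bradycardia, symptoms requiring ICU admission and mechanical ventilation, symptoms requiring repeat hospitalization, or death", alongside a list of laboratory tests.
- Section 16.1 adds that "if the study participant's condition deteriorates at any time during the study, it will be recorded as an AE".
- The SAE definition in Section 16.2 includes death, life-threatening events and "Inpatient hospitalization or prolongation of existing hospitalization".
- SAE forms are required for any serious event, "including death due to any cause whether or not related to the study drug".

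On the efficacy side, Section 2 states: "The primary end-point is a composite endpoint of mechanical ventilation or death within 4 weeks of randomization". It also lists "ICU transfer within 29 days of randomization" as a secondary endpoint of its own. No text removes these events, or COVID-19 progression generally, from the grade III-V AE/SAE endpoint.

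Section 15.1 also names three primary safety endpoints within 4 weeks: death or mechanical ventilation, grade 3 or higher transaminase elevation, and neutropenia. Each gets a rate by arm, a 95% confidence interval and its own Fisher test.

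**The concern.** A between-arm toxicity endpoint should move with the harm that the drug does. This one also moves with the benefit that the trial hopes to show. The power calculation expects death or ventilation to fall from 40% to 15%. Each such event avoided takes a patient out of the AE/SAE count unless that patient has another qualifying event, and so makes room for a patient with drug toxicity. The more effective the drug, the more toxicity the endpoint can absorb before the arms differ.

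The synopsis makes safety and tolerability a study question. A null or favourable result on this line could be cited in support of tolerability when it reflects fewer ventilations and deaths. The risk is greatest for listed toxicities with no between-arm test of their own: diarrhea, bradycardia, lymphopenia, anemia and thrombocytopenia.

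**Working it through.** **Inputs from Section 15.1.** There are 40 patients per arm. Death or ventilation is 40% on placebo and 15% on duvelisib. Placebo rates are 10% for grade 3 or higher transaminases and 24% for neutropenia. The safety stopping rule acts on an excess of 15 points (3 of 20) in any one event type, and I use 15 points as the illustrative harm. It is the plan's margin, not an observed rate.

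**The plan's own figure.** The stated power is above 80% for 40% against 15%, with 40 per arm and a two-sided 10% level. A pooled z calculation without continuity correction gives 81.5%, so the rates and sample size are read as the plan intends.

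**Assumptions.** Event types are independent, and all count as grade 3 or higher or serious. Section 15.1 does not clearly attach a grade to neutropenia, and the laboratory list in Section 16.2 does not name it, so results are also given without it. Diarrhea, other laboratory toxicities, rehospitalization and ICU admission without ventilation are left out, because the documents give no usable rates.

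**Formula.** P(any event) = 1 − product of (1 − p) over the event types.

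*With the efficacy events, as the plan has it:*
- Placebo: 1 − 0.60 × 0.90 × 0.76 = 59.0%
- Duvelisib: 1 − 0.85 × 0.75 × 0.61 = 61.1%
- Exact Fisher power: 3% at two-sided 0.05, 6% at 0.10

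*Without the efficacy events:*
- Placebo: 1 − 0.90 × 0.76 = 31.6%
- Duvelisib: 1 − 0.75 × 0.61 = 54.3%
- Exact Fisher power: 46% at 0.05, 56% at 0.10

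**How the pooled result changes with the inputs:**

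| Scenario on duvelisib | Placebo | Duvelisib |
|---|---|---|
| 15% death/ventilation, no added toxicity | 59.0% | 41.9% |
| 15%, each toxicity +10 points | 59.0% | 55.1% |
| 15%, each toxicity +15 points | 59.0% | 61.1% |
| 15%, each toxicity +20 points | 59.0% | 66.7% |
| 27.5% (half the benefit), each toxicity +15 points | 59.0% | 66.8% |
| 15%, transaminases only, 10% to 25% | 59.0% | 51.6% |
| Same, neutropenia not counted | 46.0% | 36.3% |

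The transaminase-only row is 1 − 0.85 × 0.75 × 0.76 = 51.6%. Without neutropenia it is 1 − 0.60 × 0.90 = 46.0% against 1 − 0.85 × 0.75 = 36.3%. In both, the endpoint favours duvelisib although one toxicity has risen by 15 points. At +20 points each, the pooled line moves the right way, but Fisher power is 7% at 0.05, against 70% without the efficacy events.

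**Independence.** With a Gaussian copula linking the three event types at +15 points each, the pooled rates are 53.4% against 54.9% (correlation 0.3), 47.5% against 48.2% (0.6) and 41.3% against 40.8% (0.9). The near-tie does not depend on independence.

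**Balance point.** The pooled rates are equal when the toxicity-only rate on duvelisib is 1 − 0.60 × 0.684 / 0.85 = 51.7%, against 31.6% on placebo. At the full planned benefit, about 20 points of excess on the toxicity composite are absorbed before this endpoint turns against the drug.

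**The case against.** The strongest reply is that the plan already separates toxicity from benefit. The toxicities in the illustration are two of the three primary safety endpoints, each with its own Fisher test. There the same harm appears as 10% against 25% and 24% against 39%, and benefit cannot cancel it. The interim stopping rule also works by event type: with 20 per arm, the exact chance of 3 or more excess events is 58% for transaminases and 57% for neutropenia. Secondary infection is a secondary endpoint in its own right. Section 16.1 adds tabulation by toxicity type, review by attribution, a grade 3 or higher non-hematologic proportion and discontinuations for adverse events. The IDMC reviews grade 3 and 4 events by arm every month. The pooled endpoint is one of twelve secondary items, for which Section 15.1 promises mainly descriptive statistics.

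Most of this stands. A reader might infer that the trial's safety assessment as a whole cannot tell toxicity from benefit. The documents do not support that, because the separate endpoints and the event-specific stopping rule do exactly that for the main expected toxicities.

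Three gaps remain. The separate tests are weak at 40 per arm: power at 0.05 is 33% for transaminases and 23% for neutropenia, against 46% for the two combined without efficacy events. Diarrhea, bradycardia, lymphopenia, anemia and thrombocytopenia have no named between-arm test other than the pooled one. The non-hematologic proportion does not say whether ventilation, ICU admission and death are left out, so it may share the problem.

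A second objection concerns the remedy. Section 13 lists pneumonitis and infection as duvelisib risks, and Section 3.1 likens COVID-19 infiltrates to autoimmune pneumonitis. Serious pulmonary drug toxicity could therefore surface as ventilation or ICU admission, and removing those events outright could hide it. This stands and shapes the fix.

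**Conclusion.** The point holds for this endpoint. Grade III-V AEs or SAEs, as the plan collects them, include the primary efficacy events, and benefit can cancel toxicity in the between-arm comparison. At the plan's rates with 15 points of added harm on each of two toxicities, a 23-point toxicity difference shrinks to 2 points, and Fisher power at 0.05 falls from 46% to 3%.

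The size is conditional. It rests on the full planned benefit, on the stopping margin as the size of harm, and on every event counting as grade 3 or higher. A reader might infer that any effective but toxic drug would look as safe as placebo here. That goes too far: duvelisib looks better than placebo at +10 points each, and worse at +20 points or with half the benefit. A null or favourable result on this line alone should not be cited as evidence of tolerability. The matter is an inexpensive improvement to one endpoint and to the listed toxicities without their own test. It is not a failure of the trial's safety monitoring.

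**What to change.** Keep the all-cause grade III-V AE/SAE endpoint as defined. In Section 15.1, prespecify beside it the same between-arm comparison with mechanical ventilation, ICU admission and death excluded, and show those events by arm on a line of their own. State whether neutropenia counts and at what grade. Say also whether the grade 3 or higher non-hematologic proportion in Section 16.1 includes the same events.

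Define the exclusion by event type, not by attributed cause. The AE form in Section 16.2 records relationship to study treatment, not to COVID-19, so exclusion by cause would need a new blinded adjudication. Exclude the events and not the patients, so that a ventilated patient with a grade 3 transaminase elevation still counts.

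The cost is a few lines of analysis text and one extra table. The events are already collected, and no visit or treatment changes. The limitation is that drug-related lung injury may appear only as ventilation or ICU admission, so the second line must be read beside the all-cause line and must never replace it.
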